3. OVERVIEW OF STUDY DESIGN

This is an open-label, randomised, multicentre controlled, study evaluating the safety and effectiveness of the EVARREST compared with SURGICEL in controlling mild or moderate bleeding in hepatic parenchyma or soft tissue for which standard methods of achieving haemostasis are ineffective or impractical

Eligible subjects will be randomised in a 1:1 allocation ratio to either EVARREST or SURGICEL treatment. Subjects will be followed post-operatively through discharge and at 30 days (+/-14 days) post-surgery.

Enrolment will be staggered by age. The first group enrolled will include subjects ≥ 1 years to <18 years of age and the subsequent group will include subjects from 1 month (≥ 28 days from birth) to <1 years of age. Ongoing safety assessment will ensure adequate safety monitoring occur during the staged enrolment.

4. STUDY POPULATION

4.1 General Considerations

The Investigator is expected to invite all subjects expected to meet the study entry criteria to participate in the study.

The TBS will be the only region evaluated for the primary endpoint and all secondary effectiveness endpoints. Please refer to section 7.1.3. for definition of the TBS.

The study will target to have approximately a minimum of 25% of procedures have the target bleeding site in the hepatic parenchyma and approximately a minimum of 25% of the target bleeding sites in soft tissue. Enrolment will be monitored by the sponsor and the Investigators will be notified by the sponsor once those targets have been met.

4.2 Inclusion Criteria

Pre-operative:

1. Paediatric subjects aged ≥ 28 days (≥ 1 month) to <18 years, requiring non-emergent open hepatic, abdominal, retroperitoneal, pelvic or thoracic (non-cardiac) surgical procedures;
 - i) The first 36 subjects to be enrolled will be subjects aged ≥ 1 years to <18 years.
 - ii) The next 4 subjects to be enrolled will be subjects aged ≥ 28 days to <1 year.
2. The subject's parent/legal guardian must be willing to give permission for the subject to participate in the trial, and provide written Informed Consent for the subject. In addition, assent must be obtained from paediatric subjects who possess the intellectual and emotional ability to comprehend the concepts involved in the trial. If the paediatric subject is not able to provide assent (due to age, maturity and/or inability to intellectually and/or emotionally comprehend the trial), the parent/legal guardian's written Informed Consent for the subject will be acceptable for the subject to be included in the study.

Intra-operative

3. Presence of an appropriate mild or moderate bleeding soft tissue or hepatic parenchyma Target Bleeding Site (TBS) identified intra-operatively by the surgeon;
4. Ability to firmly press trial treatment at TBS until 4 minutes after randomisation;

4.3 Exclusion Criteria

Pre-operative

1. Subjects with known intolerance to blood products or to one of the components of the study product or is unwilling to receive blood products;
2. Female subjects, who are of childbearing age (i.e. adolescent), who are pregnant or nursing;
3. Subject is currently participating or plan to participate in any other investigational device or drug without prior approval from the Sponsor;

4. Subjects who are known, current alcohol and/or drug abusers
5. Subjects admitted for trauma surgery
6. Subjects with any pre or intra-operative findings identified by the surgeon that may preclude conduct of the study procedure.

Intra-operative

7. Subject with TBS in an actively infected field (Class III Contaminated or Class IV Dirty or Infected)⁵
8. TBS is from large defects in arteries or veins where the injured vascular wall requires repair with maintenance of vessel patency and which would result in persistent exposure of the EVARREST or SURGICEL to blood flow and pressure during healing and absorption of the product;
9. TBS with major arterial bleeding requiring suture or mechanical ligation;
10. Bleeding site is in, around, or in proximity to foramina in bone, or areas of bony confine.

5. RANDOMISATION

5.1 Overview

Randomisation will be used to avoid bias in the assignment of treatment to each subject, to increase the likelihood that attributes of the subject are evenly balanced across treatment groups, and to enhance the validity of statistical comparisons across treatment groups.

5.2 Procedures

ETHICON will provide each site with computer-generated randomisation envelopes, each bearing the subject randomisation number, and containing the treatment allocation.

Treatment will be assigned randomly to each subject on a 1:1 basis to either EVARREST or SURGICEL treatment.

In the event that a potential subject fails intra-operative criteria (i.e. no TBS identified, or an intra-operative exclusion), and is not randomised to the study, the unused randomisation envelope should be returned to the series, and used for the next subject.

Given the difference between the EVARREST and SURGICEL treatment groups, it will not be possible for the surgeon to be blinded to the treatment. However, to avoid any bias in the conduct of the surgical procedure, randomisation should only take place after completion of the following steps:

1. EVARREST and SURGICEL will be prepared and available in the sterile field in the operating room, ready for administration for each patient.
2. The investigator must perform the surgical procedure according to his/her standard of care.

⁵ Appendix 1

3. Once the investigator encounters an appropriate hepatic parenchyma or soft tissue TBS related to the primary operative procedure, randomisation should immediately take place. The randomisation envelope will be opened simultaneously with starting the stopwatch.

If the subject is randomised to SURGICEL then the unused EVARREST treatment product MUST immediately be removed from the sterile field and placed for destruction. After the procedure accountability of the product should be documented.

If additional soft tissue bleeding sites requiring a topical haemostatic product are identified after the treatment of the initial target bleeding site, these bleeding sites should be treated according to the surgeon's standard of care.

6 INVESTIGATIONAL PRODUCT AND CONTROL GROUP

6.1 EVARREST Sealant Matrix / Fibrin Sealant Patch (Treatment Group)

6.1.1 Formulation

EVARREST Sealant Matrix / Fibrin Sealant Patch is a sterile bio-absorbable combination product consisting of two constituent parts—a flexible matrix and a coating of two biological components (Human Fibrinogen and Human Thrombin) embedded in a flexible composite patch component. The active side is white-to-yellowish in color and powdery in appearance; the non-active side has an embossed wave pattern.

The patch component of EVARREST consists of an oxidised regenerated cellulose (ORC) layer underlying a layer of polyglactin 910 (PG910) non-woven fibers. The PG910 layer contains the embedded biological components. The patch component provides a large surface area for the biological components and imparts inherent mechanical integrity to the product. The flexibility of EVARREST accommodates the physiological movements of tissues and organs.

Each unit of EVARREST used for this clinical trial will be 4x4 inches (10.2 x 10.2 centimeters) or 2x4 inches (5.1 x 10.2 centimeters) in size. For additional details, please refer to the Investigator's Brochure.

6.1.2 Labelling and Packaging

EVARREST is packaged in a polyester tray and lid assembly within an outer pouch composed of polyester laminated aluminium foil with an inner heat seal coating. The tray/lid assembly maintains product integrity during storage and transport. The outer aluminium pouch serves as a barrier to moisture and microbial contamination.

The aluminium pouches are packed into padded cardboard envelopes as secondary packaging.

The cardboard envelopes may be labelled with the following information as applicable:

- Name and address of manufacturer
- Protocol number
- Lot/Batch number
- Expiry date
- EudraCT number
- Storage conditions
- Statement that the product is limited for clinical trial use only

6.1.3 Shipping, Handling and Storage Conditions

Shipping conditions should be 2° to 25 °C.

Unopened packages of EVARREST should be stored at 2° to 25 °C.

Once opened, the product can remain in the sterile field throughout the surgical procedure but must be kept dry to avoid pre-activation. Unused, open product should be appropriately discarded.

Distribution of the EVARREST to the clinical sites will be performed by a qualified distribution centre with proper inventory and quality control capabilities once all the necessary documentation and approvals are obtained.

6.1.4 Preparation

EVARREST comes ready to use in sterile packages and must be handled accordingly. Only undamaged packages should be used. Once the aluminium pouch is opened, re-sterilisation is not possible. EVARREST does not require any preparation. The following procedure for opening and applying the product should be followed to ensure that the sterility of EVARREST is maintained. Note that EVARREST must be kept dry at all times prior to application to avoid pre-activation.

Please refer to the Instructions for Use for further details.

Non-sterile nurse / Study Personnel

Remove the foil pouch from the carton. Carefully peel open the foil pouch taking care to not touch the inside of the foil or the white sterile tray containing the EVARREST. Present the white tray to the scrub nurse.

Sterile nurse/field

Remove the sterile tray from inside the foil pouch. Within the sterile field, hold the tray securely in the palm of the hand, ensuring that the side with the holes is facing upwards. Using the tabs on the side of the tray, remove the top of the tray with the other hand and discard.

The lower portion of the tray contains the EVARREST with active side facing downwards. The active side is powdery and white to yellowish in colour, whilst the non-active side has an embossed wave pattern. EVARREST does not stick to gloves, forceps or any surgical instruments.

The opened EVARREST can remain in the sterile field to be available for use throughout the procedure but must be kept dry and should be discarded appropriately at the end of the procedure.

EVARREST can be carefully cut to the size and shape required with sterile scissors, avoiding excessive handling.

6.1.5 Dose, Route and Duration of Administration

For each subject, EVARREST will be available in the sterile field and ready for administration prior to randomisation. EVARREST is intended for topical use only. See application procedures in Section 7.1.3. Additional information can also be found in the Investigator's Brochure.

6.2 Investigational Product Dispensation and Accountability

A dispensing log will be kept by the designated study personnel. This log will contain information on the date of administration, subject ID and quantity of EVARREST dispensed, details of any remaining product, and subsequent destruction. The study monitor will verify these logs during the course of the study.

6.3 SURGICEL Oxidised Regenerated Cellulose (Control Group)

For this study, SURGICEL treatment will be initiated with 4 minutes of continuous manual compression following randomisation with or without gauze or sponge.

All haemostasis evaluations for the EVARREST treatment group will also be required for the SURGICEL treatment group.

6.4 Concomitant Medications

6.4.1 Topical Haemostats

The use of any other topical haemostats or fibrin sealant/fibrin sealant patch will be permitted and must be used according to the surgeon's usual practice. Details of all topical haemostats used for the subject throughout the procedure will be recorded on the Concomitant Medication CRF.

6.4.2 Documentation of Concomitant Medications

Indication and start-stop dates of concomitant medications administered from 24 hours prior to surgery up to the follow up contact or evaluation will be recorded. This will include medications used chronically (even if temporarily halted for surgery) and those medications administered as a prophylactic before, during and after surgery.

Anaesthetics used for surgery and over the counter (OTC) drugs will not be recorded as concomitant medication (with the exception of prophylactic aspirin, which should be documented). Concomitant medications used to treat Adverse Events (even if the concomitant medication is an OTC drug or nutritional supplement) must also be documented.

7 STUDY EVALUATIONS

7.1 Study Procedures

The schedule of events included in the synopsis summarizes the frequency and timing of the study procedures. Data collected for the subject during the study will be recorded in the subject's medical records, and study worksheets/source documents, as appropriate, and recorded into the eCRF.

7.1.1 Screening (Within 21 Days Prior to Surgical Procedure)

Prospective subjects will be screened within 21 days prior to surgery.

The following tests and activities will be performed at the screening visit unless existing data from within 21 days prior to surgery is available, in which case the test/activity will not be repeated. The timing of these activities may occur based on routine hospital practice but may be done up to the day of, but prior to, surgical procedure.

- Informed Consent & Assent process as applicable.
- Allocation of screening number.
- Documentation of demography (age, gender, race/ethnic origin).
- Physical examination as per normal procedure.
- Documentation of relevant medical and surgical history.

- Laboratory evaluations – these may be collected at any time within 21 days prior to surgery. Only one pre-operative laboratory evaluation is needed. The laboratory results closest to the date prior to surgery will be used.
 - Full blood count (FBC) with differential
 - Coagulation parameters to include Prothrombin Time (PT), Activated Partial Thromboplastin Time (aPTT), International Normalised Ratio (INR) and platelet count
- Review of Inclusion / Exclusion criteria to confirm subject pre-operative eligibility. In the event that a subject is not eligible, the reason will be documented on the worksheet/screening log.

7.1.2 Baseline Assessments (Within 24 Hours Prior to Procedure)

The following activities will be performed within 24 hours prior to the procedure. The timing of these activities may occur based on routine hospital practice. The Screening Visit activities may be combined with this visit.

- Review of inclusion / exclusion criteria to confirm subject pre-operative eligibility. In the event that a subject is not eligible, the reason will be documented on the worksheet/screening log.
- Documentation of all concomitant medications as stated in Section 6.4
- Documentation of any changes in medical history from the screening visit (if done on a separate visit from Baseline).
- Document subject weight and calculate maximum EVARREST units that could be used during the procedure
- Serum or urine pregnancy test (for female subjects of childbearing age)
- At least one FBC with differential, coagulation parameter testing and pregnancy test (if applicable) are needed pre-procedure. If pre-operative blood tests are repeated, only the test results closest to the date prior to surgery will be collected.

The maximum size of EVARREST to be implanted is 6.9 square cm per kilogram of body weight. Where subject's body weight allows additional pads to be placed, a maximum of four units (each unit is 4 x 4 inches (10.2 x 10.2 centimeters) of EVARREST may be implanted (left in place at the bleeding site) per subject assigned to be treated with EVARREST.

If the unit size used is 2x4 inches (5.1 x 10.2 centimeters), a maximum of eight units may be implanted (left in place at the bleeding site) per subject assigned to be treated with EVARREST (where subject's body weight allows).

Note: At least one FBC with differential, coagulation parameter testing and pregnancy test (if applicable) are needed pre-procedure. If pre-operative blood tests are repeated, only the test results closest to the date prior to surgery will be collected.

7.1.3 Surgical Procedure

The surgeon will use his / her standard surgical techniques for the surgical procedure.

Target Bleeding Site Identification

For this investigation, the target bleeding site (TBS) will be identified during the soft tissue or hepatic dissection related to the primary operative procedure. (For example, the TBS might be the retroperitoneal bed during or following nephrectomy, the area of lymph node dissection during peri-aortic node dissection, the pelvic wall during low anterior resection of the colon or in the hepatic parenchyma after a hepatic resection.)

The surgical procedure must be an open procedure to allow for appropriate EVARREST application. When patients are undergoing abdominal and thoracic (non-cardiac) procedures, open is defined as the opening of the peritoneal or pleural/thoracic cavity. The following surgical procedures are permitted to be included in this study:

- Hepatic
- Intra-Abdominal
- Intra-Thoracic (Non-Cardiac)
- Retroperitoneal
- Pelvic (Extra-peritoneal space)

Laparoscopic, thoracoscopic and other endoscopic procedures are excluded from this study.

Soft Tissue includes but may not be limited to the following tissue types:

- Muscle
- Lymphatic Tissue/lymph node beds
- Fatty tissue
- Loose Areolar Connective Tissue

For this study, the TBS will be defined as the FIRST actively bleeding site identified during the soft tissue or hepatic dissection related to the primary operative procedure with challenging mild to moderate bleeding, where conventional methods of control (i.e. suture, ligature, cautery) have been deemed ineffective or impractical, and require an alternative method to achieve haemostasis. The TBS must be a site where occlusion of the injured tissue surface blood vessels is required to achieve haemostasis. This excludes large defects in large arteries or veins where the injured vascular wall requires repair with maintenance of vessel patency and which would result in persistent exposure of the EVARREST to blood flow and pressure during healing and absorption of the product. ***EVARREST should not be used in place of sutures or other forms of mechanical ligation for the treatment of major arterial bleeding.***

The TBS area must be possible to cover with an appropriate overlap with a margin of 1-2 cm, using, a single 4 x 4 inch (10.2 cm x 10.2 cm) EVARREST or two 2 x 4 inch (5.1 cm x 10.2 cm) units of EVARREST. If two 2 x 4 inch (5.1 cm x 10.2 cm) units of EVARREST are used, there must be overlap with a margin of 1-2 cm between the 2 units of EVARREST.

As a frame of reference, the following scale of bleeding intensity will be utilised. Only target bleeding sites with mild or moderate bleeding as defined by this scale will be included:

Mild Bleeding: A TBS with a small area of capillary, arteriole or venule oozing.

Moderate Bleeding:

1. A TBS with a larger area of capillary, arteriole, or venule oozing that presents a significant challenge because of the larger area involved, increasing the volume of blood loss.

Or

2. A TBS with bleeding that is more pronounced than oozing, that could also come from a small artery or vein, but is not massive, pulsatile, and flowing.

Severe Bleeding (EXCLUDED BY THIS PROTOCOL):

Bleeding (arterial, venous, or mixed) that is rapidly flowing, pulsatile or spurting that in the surgeon's judgment requires rapid control to prevent hemodynamic consequences (e.g. hypovolemia, tachycardia, or hypotension) and could involve major volume loss which if not treated rapidly could be life threatening. EVARREST should not be used in place of sutures or other forms of mechanical ligation for the treatment of major arterial bleeding.

The TBS will be identified, and will be the only specific site or region to be evaluated for time to haemostasis in this clinical study. The following activities will be performed, and information will be collected, during the surgical procedure:

- Review of inclusion and exclusion criteria to confirm intra-operative. In the event that a subject is no longer eligible, the reason for the screen failure will be documented in the source documentation and screening log
- Haemostatic methods used at TBS prior to EVARREST application (none (other methods are impractical), suture, ligation, cautery, other)
- Primary Operative Procedure information: Abdominal resection, retroperitoneal tumour resection, hepatic resection or other (specify)
- TBS location information: hepatic, abdominal, pelvic, retroperitoneal, thoracic (non-cardiac or other location (specify)
- Type of bleeding (mild or moderate)
- Size of TBS (length, width, area)
- TBS tissue type: hepatic parenchyma, loose areolar connective tissue, fat, lymphatic tissue/lymph node beds, muscle or other (specify)
- Liver only TBS assessment (See 7.1.3.3)
- Documentation of concomitant medications as outlined in Section 6.4
- Total number of units used

Pre-Randomisation Procedures:

- EVARREST and SURGICEL will be prepared and available in the sterile field in the operating room, ready for administration for each subject.
- When the surgeon encounters the first appropriate TBS with mild or moderate bleeding in the hepatic parenchyma or soft tissue related to the primary operative procedure where conventional methods of control (i.e. suture, ligature, cautery) are ineffective or impractical, the subject can be considered for randomisation.

Randomisation:

- Once intra-operative eligibility is confirmed, and the TBS identified, the randomisation envelope will be opened while simultaneously starting the stopwatch will be immediately started, and recording the time on the wall clock (T_0).

For Subjects Randomised to EVARREST

The maximum size of EVARREST to be implanted is 6.9 square cm per kilogram of body weight. Where subject's body weight allows additional pads to be placed, a maximum of four units of the 4 x 4 inches (10.2 x 10.2 centimeters) EVARREST or a maximum of eight units of the 2 x 4 inches (5.1 x 10.2 centimeters) EVARREST may be implanted (left in place at the bleeding site) per subject assigned to be treated with EVARREST.

The size of the EVARREST applied should be sufficient for coverage of the entire TBS, and should overlap the TBS with a margin of 1-2 cm.

The surgeon will immediately apply firm continual manual compression over the entire bleeding area until 4 minutes from randomisation. The surgeon may use a surgical sponge (laparotomy pad or surgical gauze) to assist in providing adequate even pressure over the entire surface area.

The absolute time to haemostasis will be recorded, which is defined as the time elapsed from randomisation to the last moment in time at which detectable bleeding at the TBS is observed, i.e., complete haemostasis at the TBS.

Haemostasis will also be assessed at 4 minutes and 10 minutes and at initiation of final closure, post-randomisation for all subjects.

EVARREST should not be removed once bleeding has been stopped.

If breakthrough bleeding occurs at the TBS at any time after application, the surgeon may re-treat with EVARREST if clinically appropriate, or revert to their standard of care. Any EVARREST re-treatment must be performed according to the Investigator's Brochure.

EVARREST Re-treatment

- If the surgeon finds the EVARREST was not applied properly (if there are folds, creases or crimps in the patch) the EVARREST pad should be removed and a new EVARREST pad applied as per the Investigator's Brochure. No matter the point of application, haemostasis must be assessed at 4 and 10 minutes from randomisation.
- If bleeding is due to insufficient coverage of the bleeding area, additional patches may be applied. Ensure that the edges overlap (by approximately 0.5 to 1 inch or 1 to 2 cm) with the existing patch.
- If bleeding is due to incomplete adherence to the tissue (where bleeding persists under the dressing), remove the patch and use a new one.
- If bleeding still occurs during or after the specified duration of compression, remove the used EVARREST and inspect the bleeding site. If no other primary hemostatic measures (i.e., standard surgical techniques) appear to be required, repeat the application procedure above with a new EVARREST.

EVARREST can only be used on a single TBS to be evaluated. If additional soft tissue/hepatic bleeding sites are identified, the surgeon should treat according to their standard of care.

For Subjects Randomised to SURGICEL

The control treatment group will be initiated with application of SURGICEL as per its Instructions for Use.

The surgeon will immediately apply firm continual manual compression over the entire bleeding area until 4 minutes from the time of randomisation.

The absolute time to haemostasis will be recorded, which is defined as the time elapsed from randomisation to the last moment in time at which there is detectable bleeding at the TBS is observed, i.e., complete haemostasis at the TBS.

Haemostasis will also be assessed at 4 minutes and 10 minutes and at initiation of final closure, post-randomisation for all subjects.

Additional SURGICEL may be used at the target bleeding site prior to the 4 minute time point if the surgeon finds the SURGICEL was improperly applied.

If haemostasis in the SURGICEL group is not achieved, or if bleeding requiring re-treatment at the TBS occurs anytime after the 4-minute assessment, the surgeon must control bleeding according to their standard of care.

HAEMOSTASIS ASSESSMENT (TIME TABLE):

T₀	Start time when randomisation envelope is opened
T_{APP}	Time when haemostatic product is initially applied with manual compression
T₄	TBS Bleeding assessment 4 minutes following randomisation. Note: Manual compression must be maintained from application until this initial assessment.
T₁₀	TBS Bleeding assessment 10 minutes following randomisation.
T_{ABS}	Absolute time to haemostasis; as defined as the absolute time elapsed from randomisation to the last moment in time at which there is detectable bleeding at the TBS

7.1.3.1 Adverse events from start of randomisation, including any complications potentially related to bleeding and/or thrombotic events.

7.1.3.2 Additional procedural and hospital stay information will also be recorded including surgery procedural times, blood product usage, blood transfusions, ICU time, estimated blood lost, cell saver use, surgical procedure/reason for surgery and alternative/additional methods used to achieve haemostasis (if applicable).

7.1.3.3 Additional surgical details will be captured for a liver only TBS, including estimated total transected plane area; estimated transected plane area treated (0-25%, 26-50%, 51-75%, 76-100%); reason for, type and location of liver resection; hepatic parenchymal classification/type; and surgeon description of bleeding site at the TBS (area, density, arterial/venous/mixed, and characterisation of intensity of flow).

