At least 40 qualified paediatric subjects with an appropriate mild or moderate bleeding Target Bleeding Site (TBS) will be randomised in a 1:1 allocation ratio to either EVARREST or SURGICEL (control). Absolute time to haemostasis will be assessed as well as haemostasis at 4 and 10 minutes from randomisation.

Enrolment will be staggered by age (as required by the European Medicines Agency (EMA) Paediatric Committee). The first 36 subjects enrolled will be aged ≥ 1 years to <18 years of age. Enrolment of a subsequent group will include 4 subjects from 1 month (≥ 28 days from birth) to <1 year of age will follow. Ongoing safety assessment will ensure adequate safety monitoring occur during the staged enrolment.

Subjects will be followed post-operatively through hospital discharge and at 30 days (+/-14 days) post-surgery.

TBS DEFINITION: The Target Bleeding Site (TBS) will be defined as the first accessible mild or moderate bleeding site identified in the hepatic parenchyma or soft tissue, where conventional methods of controlling bleeding are ineffective or impractical, and is amenable to manual compression. The TBS must be a site where occlusion of the injured tissue surface blood vessels is required to achieve haemostasis.

The TBS must be an area that can have firm pressure applied and maintained continuously until 4 minutes after randomisation, and to which EVARREST can be applied with a margin of 1-2cm. (Refer to Investigator's Brochure).

EVARREST should not be used on large defects in arteries or veins where the injured vascular wall requires repair with maintenance of vessel patency and which would result in persistent exposure of the EVARREST to blood flow and pressure during healing and absorption of the product. EVARREST should not be used in place of sutures or other forms of mechanical ligation for the primary treatment of major arterial bleeding.

BLEEDING

SEVERITY:

Mild Bleeding: a TBS with a small area of capillary, arteriole or venule oozing

Moderate Bleeding: a TBS with a larger area of capillary, arteriole, or venule oozing that presents a significant challenge because of the larger area involved, increasing the volume of blood loss,

Or

A TBS with bleeding that is more pronounced than oozing, that could also come from a small artery or vein, but is not massive.

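### The bleeding-site size limit in Protocol 7.1.3 is not tied to the 6.9 cm²/kg implant ceiling, so in children under about 15 kg an eligible site may not be coverable with a 1 cm margin inside the ceiling

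*Protocol*

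**What the plan says.** **Site size limit.** Section 7.1.3 says the site "must be possible to cover with an appropriate overlap with a margin of 1-2 cm, using, a single 4 x 4 inch" unit (10.2 x 10.2 cm), or two 2 x 4 inch units (5.1 x 10.2 cm each) that overlap by 1-2 cm. The sentence has no weight term. Section 4.1 sends the reader to 7.1.3 for the TBS definition.

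**Implant ceiling.** Section 7.1.2 states: "The maximum size of EVARREST to be implanted is 6.9 square cm per kilogram of body weight". At baseline the site must "Document subject weight and calculate maximum EVARREST units that could be used during the procedure". Within 7.1.3 the ceiling is repeated only in the instructions for subjects already randomised to EVARREST. The same instructions say the EVARREST applied "should be sufficient for coverage of the entire TBS, and should overlap the TBS with a margin of 1-2 cm".

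**Order of events.** "Once intra-operative eligibility is confirmed, and the TBS identified, the randomisation envelope will be opened", and the stopwatch starts at that moment. TBS length, width and area are on the list of data collected during surgery, with no instruction to set them against the weight-based maximum.

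**Related provisions.** Section 6.1.4 says "EVARREST can be carefully cut to the size and shape required with sterile scissors". The synopsis TBS definition requires a site "to which EVARREST can be applied with a margin of 1-2cm" and refers to the Investigator's Brochure. Inclusion 3 asks for an appropriate TBS. Exclusion 6 lets the surgeon exclude a child for findings that may preclude the study procedure. SURGICEL is applied under its own Instructions for Use, and the protocol gives no area ceiling for it. SAP Section 7 summarises implanted EVARREST in cm² per kg.

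**The concern.** Three instructions meet in the smallest children: the site may be as large as one 4 x 4 inch unit can cover, the patch should cover the whole site with a 1-2 cm margin, and the patch may not exceed 6.9 cm²/kg. For a large enough site in a light enough child they cannot all be met.

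Timing and asymmetry are what matter. If the conflict is noticed only after the envelope is opened, the stopwatch for the primary endpoint is running and the child is bleeding. It can arise only in a child assigned to EVARREST. The choices then are a margin below 1 cm, incomplete coverage in extreme cases, or a breach of the ceiling. Adding a patch, which 7.1.3 allows when coverage is insufficient, may not be open if the ceiling is already used up.

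The infant group is small. Four subjects under 1 year are planned, so 1:1 allocation implies about two on EVARREST, and the primary endpoint is summarised for that group by treatment (Protocol 8.3.2, SAP 8.2). One compromised application could be half of that cell.

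**Working it through.** The plan gives no figure of its own to reproduce. The check is area arithmetic.

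**Inputs.** Ceiling 6.9 cm²/kg (7.1.2, 7.1.3). Unit sizes 10.2 x 10.2 cm and 5.1 x 10.2 cm (6.1.1). Margin 1-2 cm (7.1.3). Neither document gives body weights or expected site sizes. As an assumption, infants under 1 year weigh about 4-10 kg.

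**1. Weight at which a whole unit reaches the ceiling** (unit area / 6.9)
- 4 x 4 inch: 10.2 x 10.2 = 104.04 cm²; 104.04 / 6.9 = 15.08 kg.
- 2 x 4 inch: 5.1 x 10.2 = 52.02 cm²; 52.02 / 6.9 = 7.54 kg.

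**2. Largest site within the size limit**
- One 4 x 4 inch unit: (10.2 - 2)² = 67.24 cm² at a 1 cm margin; (10.2 - 4)² = 38.44 cm² at 2 cm.
- Two 2 x 4 inch units side by side, 1 cm overlap, 1 cm margin: (9.2 - 2) x (10.2 - 2) = 59.04 cm².

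**3. Largest square site coverable inside the ceiling:** (√(6.9 x kg) - 2 x margin)²

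| Weight | Ceiling (cm²) | 1 cm margin (cm²) | 2 cm margin (cm²) |
|---|---|---|---|
| 5 kg | 34.5 | 15.0 | 3.5 |
| 8 kg | 55.2 | 29.5 | 11.8 |
| 10 kg | 69.0 | 39.8 | 18.5 |
| 12 kg | 82.8 | 50.4 | 26.0 |
| Size limit, one 4 x 4 inch unit, any weight | – | 67.2 | 38.4 |

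**4. Weight needed for a given square site, 1 cm margin:** (side + 2)² / 6.9
- 3 x 3 cm: 25 / 6.9 = 3.6 kg
- 4 x 4 cm: 36 / 6.9 = 5.2 kg
- 5 x 5 cm: 49 / 6.9 = 7.1 kg
- 6 x 6 cm: 64 / 6.9 = 9.3 kg

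**5. Round sites, patch cut to shape, 1 cm margin:** π x ((diameter + 2) / 2)² / 6.9
- 5 cm across: π x 3.5² = 38.5 cm²; 38.5 / 6.9 = 5.6 kg.
- 8.2 cm across, the largest one 4 x 4 inch unit can cover: π x 5.1² = 81.7 cm²; 81.7 / 6.9 = 11.8 kg.

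Cutting to shape therefore lowers the threshold from 15.1 to 11.8 kg for a round site but does not remove the conflict.

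**6. What gives way**
- A 5 x 5 cm site at 6 kg: ceiling 6.9 x 6 = 41.4 cm², margin left (√41.4 - 5) / 2 = 0.72 cm. The site is fully covered with a reduced margin.
- Incomplete coverage is forced only when the site itself exceeds 6.9 x kg: 34.5 cm² at 5 kg, 55.2 cm² at 8 kg. For the largest site within the limit, 67.24 / 6.9 = 9.74 kg, so it cannot occur above that weight.

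**The case against.** The strongest reply is that the rules, read together, already cover this. A site that cannot be covered with the required margin within the child's maximum is arguably not one "to which EVARREST can be applied with a margin of 1-2cm". The maximum is worked out before surgery, when allocation is unknown, and its natural use is to inform the surgeon. Inclusion 3 and exclusion 6 give a route to decline the site. This stands in part: a careful surgeon has both the information and the discretion. But none of these clauses mentions weight or the ceiling, and the one explicit size rule, in 7.1.3, admits the site.

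A second reply is that the rules differ in force: the ceiling is a maximum, while coverage and margin are worded as what should be done, so the margin yields. That is a fair reading and agrees with step 6. It does not explain why the compromise should be found after allocation, in one arm.

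Third, the Investigator's Brochure and Instructions for Use may give sizing guidance. They were not available here, so this stays open.

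A reader might infer that EVARREST cannot be used at all below 7.5 kg, because the baseline maximum would be zero whole units of either size. The documents do not support that. The ceiling is stated as an area, nothing requires whole units, and "EVARREST can be carefully cut to the size and shape required with sterile scissors". A 3 x 3 cm site complies from 3.6 kg.

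**Conclusion.** The gap is real and narrow. The size limit and the dosing ceiling are not reconciled, and no stated step reconciles them before randomisation. The conflict is confined to the larger eligible sites in children under about 15 kg (about 11.8 kg for a round site), and its usual consequence is a margin below 1 cm. Forced incomplete coverage needs both a child under 9.7 kg and a site close to the size limit.

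A reader might go further and infer bias in time to haemostasis or selective per-protocol exclusions. The documents do not show either. They give no weights or expected site sizes, so the number affected cannot be estimated. Affected children stay in the FAS, and in the Safety set if treated. The primary analysis is descriptive on the FAS. The SAP's cm²/kg summary would reveal a breach of the ceiling, but only afterwards.

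The point is still worth correcting, because it concerns a dosing ceiling in the smallest children and can be settled before randomisation. It rests on the ceiling and unit sizes as stated, a 1 cm minimum margin, and the assumption that infants under 1 year weigh about 4-10 kg.

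**What to change.** **In 7.1.3,** keep the existing physical-fit test and add a condition for all subjects before the envelope is opened: the patch needed to cover the TBS with at least a 1 cm margin must not exceed 6.9 x body weight (kg) cm². Take the patch as cut to the shape of the site, and count any overlap between units as implanted area. The surgeon's estimate against the pre-calculated maximum is enough.

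**In 7.1.2,** record the baseline maximum in cm² as well as in units.

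Two details matter. The fit test must stay, because an area test alone would admit awkward shapes: an 11 x 4 cm site needs 13 x 6 = 78 cm², less than one unit's 104.04 cm², yet fits neither one 4 x 4 inch unit nor two overlapped 2 x 4 inch units. And the area should follow the shape of the site: a length-by-width rectangle would ask 49 cm² (7.1 kg) for a 5 cm round site that needs 38.5 cm² (5.6 kg), and would turn away treatable infants.

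**Cost.** One eligibility line and one wording change. Weight and TBS dimensions are already collected, and 5.2 already returns the unused envelope to the series when intra-operative criteria fail. The downsides are a brief size estimate at a bleeding site before randomisation, and a few small children with larger sites becoming ineligible, which may slow infant enrolment slightly.
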